6.5 Planned analyses prior to end of study

6.5.1 Safety

The DSMB will have access to unblinded safety data at the time of planned reviews and upon request of the DSMB may review additional analyses. Operating details are specified in the DSMB charter. A scheduled interim safety analysis at midpoint will be performed.

The safety and protocol adherence review team (SPART) will review all clinical and laboratory safety data during the course of the study, at least every 3 months. The site teams are responsible for regularly monitoring all Adverse Events and documenting reportable AEs to the DCC and CCC for review by the SPART. The SPART will include CCC PIs (Drs. [name], [name], [name], and [name]), Clinical Site Manager [name], and Clinical Trial Project Manager/Site Monitoring Manager [name]. Meetings of the SPART (by videoconference or teleconference) will occur regularly, and will not require attendance of all team members at each meeting. The SPART is responsible for the review of the clinical safety reports, discordant CMV serostatus test results (LFA versus CLIA test), and protocol violations, as well as communication with the IRB, NHLBI executive secretary, and DSMB as outlined in Figure 11.1.

6.5.1.1 Interim safety analysis.

It is expected in this trial that approximately 20% or approximately = 100 of the 500 participants will have death events relative to the safety endpoint. A two-sided interim safety analysis is planned to be performed at the midpoint, either at the 50th event or when 50% of participants ($n = 250$) are randomized, whichever occurs earlier.

Guidelines for early termination at the interim analysis due to concerns on the safety endpoint should (i) adjust for the nature of interim monitoring that involves repeated testing over time, (ii) reflect particular caution given the relative benefit-to-risk profile of the two arms.

Specifically, a recommendation for stopping will be based on strong evidence for the hazard ratio (treatment/placebo, HR) of death to be less than 1 or greater than 1. The O'Brien-Fleming “upper boundary” will be used to establish if an elevated event rate in the intervention group preserves the (one-sided) 0.025 false positive error rate relative to the hypothesis:

H_0 : the event rate for the intervention group relative to control ≤ 1.00 , or $HR \leq 1$.

The O'Brien-Fleming “lower boundary” will be used to establish if an elevated event rate in the control group preserves the (one-sided) 0.025 false positive error rate relative to the hypothesis:

H_1 : the event rate for the control group relative to intervention ≤ 1.00 , or $HR \geq 1$.

For illustration, Table 6.5.1-1 below presents the O'Brien-Fleming boundaries for the hazard ratio (HR) estimates that would lead to rejection of H_0 at the interim analysis performed when one has observed 50% and 100% of the trial's expected total of 100 death events.

Table 6.5.1-1: Interim analysis assumptions

Information Fraction (% of Total Events)	Reject H_0 : HR ≤ 1.00	Nominal one-sided p-values for rejection of H_0	Reject H_1 : HR ≥ 1.00
50% (50 events)	≥ 2.316	$P \leq 0.0015$; $Z = 2.97$	≤ 0.432
100% (100 events)	≥ 1.480	$P \leq 0.025$; $Z = 1.96$	≤ 0.676

Observe that, for the total of 50 events at the interim analysis, to reach the O'Brien-Fleming boundary for a lower death rate in the intervention group, the control group would need to have at least 20 excess events (15 in intervention group versus 35 in the control group) at the 50% information fraction. Similarly, to reach the O'Brien-Fleming boundary for a lower death rate in the control group for the total of 50 events at the interim analysis, the intervention group would need to have at least 20 excess events (15 in control group versus 35 in the intervention group) at the 50% information fraction. The Lan-DeMets implementation of the O'Brien-Fleming guideline will be used to provide flexibility in the timing and number (in the case of unplanned DSMB meetings) of interim analyses [100].

An efficacy analysis (of the primary endpoint) will also be conducted at the time of interim look. Although no formal stopping rule will be implemented for either efficacy or futility, number of participants (or outcome data) needed to change the direction of the observed treatment effect will be estimated at the time of the interim analysis, which is required for the DSMB's consideration

of the data. Additionally, at the time of the interim analysis, variance of the actual data will be assessed in accordance with the assumptions made in the sample size calculations.

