4. INTERIM ANALYSIS AND DATA MONITORING COMMITTEE

One interim analysis was planned and conducted after 50 deaths. The primary purpose of the interim analysis was to evaluate safety, efficacy, and sample size assumptions. This analysis included an assessment of the primary outcome (RSFDs) and mortality.

The interim analysis was conducted by the unblinded statistical team and reviewed by the independent Data and Safety Monitoring Board (DSMB). Based on pre-specified stopping boundaries and overall risk-benefit assessment, the DSMB recommended continuation of the trial without modification. No additional interim analyses were performed.

DSMB meetings were conducted on the following dates:

DSMB	1/10/2022
DSMB	7/8/2022
DSMB	8/30/2022
DSMB	1/26/2023
DSMB	8/11/2023
DSMB	2/8/2024
Interim Analysis	7/8/2024
DSMB	10/1/2024

The trial was paused for enrollment on July 22, 2022, to allow the DSMB time to review the updated dataset, and enrollment resumed on September 9, 2022. A closed enrollment decision was later made by NHLBI due to safety and futility concerns following the last DSMB meeting on October 1, 2024.

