9. SAFETY ANALYSES

A summary table of MedDRA-coded adverse events (AEs) will be generated, displaying the frequency and percentage of participants experiencing each AE by treatment group, system organ class (SOC), and preferred term. In addition, a comprehensive listing of all reported AEs will be provided. This listing will include onset date, verbatim term, MedDRA code, SAE/EAE classification, study day, severity grade, relationship to study drug, outcome, and duration (in days).

Deaths will be summarized separately by treatment group, as described in Section 2.2. A Kaplan–Meier survival analysis will be conducted to estimate the time-to-death distribution for each arm. Survival curves will be compared using the log-rank test. A Cox proportional hazards model will also be used to estimate the hazard ratio (HR) and 95% confidence interval (CI) for mortality between groups, adjusting for baseline creatinine clearance. In addition, subgroup analyses will be conducted stratified by baseline creatinine clearance (≥ 60 vs. < 60 mL/min).

Survival analyses will be performed across multiple time windows: through Day 28 and Day 180 (± 42 days). Participants lost to follow-up will be censored at their last known survival date.

To further explore potential differences in mortality risk across treatment phases, an interaction analysis will be conducted between treatment assignment and treatment period (during-treatment vs. post-treatment). This analysis will help assess whether the effect of treatment on mortality differs between the period of active drug administration and the post-treatment period.

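### The 100-death row of the illustrative mortality boundary table (protocol Table 6.5.1-1) is the unadjusted single-look value, and the SAP states no final mortality level in its place

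*Combined protocol and SAP*

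**What the plan says.** Protocol section 6.5.1.1 expects that "approximately 20% or approximately = 100 of the 500 participants will have death events". It plans one formal look: "A two-sided interim safety analysis is planned to be performed at the midpoint", which falls "either at the 50th event or when 50% of participants ($n = 250$) are randomized, whichever occurs earlier". It asks that any stopping guideline allow for repeated testing.

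Two one-sided boundaries follow. The upper one, for harm, "will be used to establish if an elevated event rate in the intervention group preserves the (one-sided) 0.025 false positive error rate". The lower one, for benefit, "will be used to establish if an elevated event rate in the control group preserves the (one-sided) 0.025 false positive error rate".

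Table 6.5.1-1, introduced as an illustration, has two rows:

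- 50 deaths: Z = 2.97, one-sided p <= 0.0015, HR >= 2.316 or <= 0.432.
- The row that begins "100% (100 events": Z = 1.96, one-sided p <= 0.025, HR >= 1.480 or <= 0.676.

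The text after the table says that the Lan-DeMets version of the O'Brien-Fleming guideline will be applied. It sets no formal efficacy or futility stopping rule for the primary endpoint.

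Protocol section 14.5 leaves the interim monitoring guidelines to the SAP. SAP section 4 reports the look as done: "One interim analysis was planned and conducted after 50 deaths". It refers to pre-specified boundaries but prints none. For the final mortality analysis, SAP section 9 says "Survival curves will be compared using the log-rank test" and adds a Cox model. Section 10 item 3 repeats this through Day 28 and Day 180. Neither section gives a significance level.

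**The concern.** If 0.025 is the total error allowed in each direction and about 0.0015 of it is spent at the interim look, the final critical value must be stricter than the single-look 1.96. The table leaves it at 1.96. The two rows therefore cannot both stand beside the stated error rate, and the last row does not follow from the spending method named in the same section.

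What is at stake is the cut-off for the final mortality comparison. The table holds the only final mortality cut-off in either document. A reader who wants the final level will find 1.96 there, or will assume the usual two-sided 0.05 because the SAP is silent.

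**Working it through.** **Inputs** (protocol 6.5.1.1 unless noted): one-sided error 0.025 per direction; looks at 50 and 100 deaths, so the information fraction is t = 0.5; Z = 2.97 and then Z = 1.96; 1:1 allocation (protocol 9.7).

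**1. Reproduce the table.** With equal allocation and d deaths, the HR at the boundary is exp(2Z/√d).

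- 50 deaths: exp(2 × 2.97/√50) = 2.316, reciprocal 0.432; one-sided p = 0.00149.
- 100 deaths: exp(2 × 1.96/√100) = exp(0.392) = 1.480, reciprocal 0.676; one-sided p = 0.0250.

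All cells reproduce. The last row was therefore computed from 1.96 itself. It is not a rounded form of an adjusted value, because 1.968 would print as 1.482.

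**2. Check the interim row.** One-sided Lan-DeMets spending of the O'Brien-Fleming type is 2 − 2Φ(2.2414/√t). At t = 0.5 this is 0.001525, so Z = 2.963. The printed 2.97 and 0.0015 agree with it to rounding.

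**3. Overall error of the two rows together.** The two statistics are correlated √0.5 under the null.

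- P(Z₁ ≥ 2.97) = 0.00149
- P(Z₁ < 2.97 and Z₂ ≥ 1.96) = 0.02399
- Sum = 0.02548 per direction, or 0.0510 two-sided

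A simulation of 20 million pairs gave 0.02550 per direction. The stated figure is 0.025, so the excess is about 0.0005.

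**4. The final value that holds 0.025.**

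| Scheme | Interim Z | Final Z | Final one-sided p | Final HR |
|---|---|---|---|---|
| Interim kept at 2.97 | 2.97 | 1.968 | 0.0245 | 1.482 / 0.675 |
| Lan-DeMets, O'Brien-Fleming type | 2.963 | 1.969 | 0.0245 | 1.482 / 0.675 |
| Classical two-look O'Brien-Fleming | 2.797 | 1.977 | 0.0240 | 1.485 / 0.673 |

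None of these returns 1.96 at the end.

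**5. If the final count is not 100.** The documents do not give the final number of deaths. The range below is an assumption. It keeps the interim at 50 deaths with Z = 2.97 and uses correlation √(50/D), where D is the final count.

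| Final deaths (assumed) | Final Z | Two-sided p | One-sided error if 1.96 is used |
|---|---|---|---|
| 70 | 1.962 | 0.0497 | 0.0251 |
| 100 | 1.968 | 0.0490 | 0.0255 |
| 150 | 1.974 | 0.0484 | 0.0258 |

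**6. If the look had come earlier.** The protocol also allowed the look at 250 randomized. At an assumed 40% or 30% information with the matching Lan-DeMets interim boundary, a final 1.96 gives 0.0251 or 0.0250. SAP section 4 says that the look came after 50 deaths, so the 50-death case is the relevant one.

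**The case against.** The strongest reply is that the plan already names the right method. The table is offered as an illustration, the section asks for adjustment for repeated looks, and Lan-DeMets spending applied as written gives about 1.969 at 100 deaths. This stands, and it limits the point: one illustrative row disagrees with the operative method. It does not remove the point, because the row is meant to show that method's result and neither document prints another final mortality cut-off.

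The second reply is size. HR 1.480 becomes 1.482. On a simple death-split reading, the arm with more deaths needs 1.480/2.480 = 59.7% or 1.482/2.482 = 59.7% of 100 deaths, so either cut-off calls for a 60/40 split. This stands too. Nor is the error the sum 0.0015 + 0.025 = 0.0265: the two rejection regions overlap by about 0.0010, which leaves 0.0255.

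Third, on the harm side a slightly lenient final cut-off makes excess deaths marginally easier to flag. That is true, but the section claims 0.025 in both directions.

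A reader might also infer that this row bore on the closing of enrollment. The documents do not support that. SAP section 4 says that the monitoring board recommended continuation after the interim analysis. It places the closure after a later meeting, on safety and futility grounds, and nothing ties it to the 100-death row. The row that governed the formal look is correct.

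Nor can one say that the SAP will test at 1.96. It states no level and does not refer to the table. The supportable criticism is that the level is missing.

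**Conclusion.** The 100-death row is wrong as printed. It is the single-look value, and with the interim row it gives about 0.0255 one-sided per direction (0.051 two-sided) against a stated 0.025. At 50 and 100 deaths the matching final value is Z of about 1.968 to 1.969, one-sided p 0.0245. The 50-death row is right.

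The result assumes two looks only, at 50 and 100 deaths, equal allocation, and the usual large-sample normal form of the log-rank statistic. Over an assumed 70 to 150 final deaths, the error with 1.96 stays above 0.025 but does not exceed 0.0258. Further unplanned formal looks would raise it.

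Two stronger readings go too far. A reader might infer that mortality error is uncontrolled by design; the named spending method, if applied, controls it. A reader might also infer that the primary test is affected; this boundary concerns deaths only, and the protocol sets no formal efficacy or futility stopping rule for respiratory-support-free days. The correction is worth making but has low priority.

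**What to change.** - **Protocol Table 6.5.1-1, 100% row:** change to Z = 1.969 (1.968 if the interim is held at the rounded 2.97), one-sided p <= 0.0245, HR >= 1.482 or <= 0.675. Note that the row holds for exactly 100 deaths and that the final boundary follows from the error already spent.
- **SAP section 9 and section 10 item 3:** add one sentence. It should name the monitored mortality comparison (Day 28 or Day 180, since both are analysed) and say that it is tested at the Lan-DeMets level left after the 50-death look, recomputed from the actual number of deaths. That level is about 0.049 two-sided at 100 deaths, and 0.0497 to 0.0484 for 70 to 150 deaths.

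The cost is one table row and one SAP sentence. No new data, extra participants or change of method is needed, and the final mortality threshold becomes very slightly stricter.

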6.5.2 Other endpoint analyses

Distribution will be limited to those with a need to know, for informing future trial-related decisions. To guarantee the unrestricted performance of its task, the DSMB may receive the individual study morbidity and mortality data from an unblinded statistician. The DSMB will have access to unblinded safety data at the time of planned reviews and upon request of the DSMB may review additional analyses. Any analyses conducted prior to the end of the study should not compromise the integrity of the trial in terms of participant retention or safety or immunogenicity endpoint assessments.

6.5.3 Sample size re-estimation plan

Considering that there is no substantial literature on the distribution of RSFDs, our trial design relies on GRAIL Phase 2 data on VFDs instead and our belief that variability in RSFDs will be similar to that of VFDs. However, in case it happens that variance of RSFDs is substantially larger than that of VFDs (which can happen for a variety of reasons including the fact that RSFDs is expected to be measured on a wider population than those who typically only require ventilation, which may introduce additional sources of variability), the common SD used in the sample size determination (Section 6.1.1) for the study may not reflect the actual value. To ensure the study remains adequately powered, the assumption of variability will be checked when the study is halfway done, ie, when endpoints for $N^* = 250 \sim 50\%$ of total initially planned sample size subjects (500) have been measured. Specifically, total variance will be calculated in a blinded way using the following approach, similar to the one proposed by Kieser and Friede as well as Zucker et al [101, 102].

$$\hat{\sigma}^2 = \frac{1}{N^* - 1} \sum_{j=1}^{N^*} (RSFD_j - \bar{RSFD}_{N^*})^2 - \frac{N^*}{4(N^* - 1)} \Delta^2$$

Where N^* : total number of subjects at re-assessment; $= N/2$ where $N = 2n$ is total sample size in the study

$RSFD_j$: RSFDs in patient j in the reassessment.

\bar{RSFD}_{N^*} : average of $RSFD_j, j = 1, \dots, N^*$

Δ : expected difference in RSFDs between the arms (based on GRAIL Phase 2 data on VFDs)

Further investigation done by Keiser and Friede[101] indicates that this method has little impact on the type I error of the test for superiority. Therefore, no type I error adjustment needs to be made. The formula for blinded estimation of variance given above depends on the assumed treatment effects. It was noted that if the treatment effect is mis-specified, the estimated variance will be biased and may be under-estimated. However, as pointed by Kieser and Friede, such bias is generally negligible in most clinical trial situations.

If the estimated pooled SD from all available subjects at sample size re-assessment is considerably larger than our assumption of 9.4 days, sample size will be recalculated based on the estimated SD from the re-assessment using a similar approach as described in Section 6.1.1. Table 6.5.3 below provides details on the sample size re-assessment under the same targeted power (85%), the same treatment differences (2.74 RSFDs), and numbers of additional subjects needed for the larger SD values. The blinded variance estimation will be performed by one of the blinded statisticians on the trial. In work by Laterre et al [83], ventilator and vasopressor free days

within 30 days had an estimated SD around 13 and we suspect SD of our RSFD primary endpoint would not go beyond that.

Table 6.5.3: Sample size re-assessment to achieve 85% power

Estimated SD	Sample size per arm	Adjusted Sample size per arm	Total Sample Size	Overall sample size increase
≤ 9.4 days	213	250	500	0
9.8 days	231	271	542	42
10.2 days	250	293	586	86
10.6 days	270	317	634	134
11 days	291	341	682	182
11.4 days	312	366	732	232
11.8 days	334	392	784	284
12.2 days	357	419	838	338
12.6 days	381	447	894	394
13 days	406	476	952	452

7 SELECTION AND WITHDRAWAL OF SUBJECTS

7.1 Study population

Five hundred adults will be randomized in a 1:1 ratio to receive either the study drug or placebo. All patients entered into this study will have established respiratory failure associated with sepsis. By virtue of their need for respiratory support (as defined in Section 4.1.1) within an intensive care unit (ICU), all patients will be considered critically ill.

Final eligibility determination will depend on results of laboratory tests, medical history, and physical examinations. Those determined to be eligible, based on the inclusion and exclusion criteria, will be enrolled in the study. Investigators should always use good clinical judgment in considering a subject's overall appropriateness for trial participation. Some subjects may not be appropriate for enrollment even if they meet all inclusion/exclusion criteria because medical, psychiatric, social, or logistic conditions may make evaluation of safety and/or efficacy difficult.

Duration of participation in the study by individual patients will be 180 days.

7.2 Randomization

Patients meeting inclusion and exclusion criteria will be randomized to standard ICU care (including standard lung protective ventilation and weaning protocols, if mechanically ventilated) + intervention or placebo.

7.3 Inclusion criteria

1. Subject/next of kin informed consent
2. Age \geq 18 years
3. CMV IgG seropositive by lateral flow assay (LFA) or standard serologic methods
4. Receiving care from an ICU team/service
5. Acute respiratory failure as defined in Section 4.1.1.
6. Expected to require respiratory support for at least 2 more days after randomization
7. Infection confirmed or suspected by the treating clinician and felt to be causing or contributing to acute respiratory failure (Respiratory failure associated with infection confers at least 2 SOFA points above assumed baseline SOFA score of 0, thereby meeting Sepsis-3 definition).

7.4 Exclusion criteria

1. Known or suspected immunosuppression, including:
 - a. HIV+ (i.e. prior positive test or clinical signs of suspicion of HIV/AIDS; a negative HIV test is not required for enrollment)
 - b. stem cell transplantation:
 - i. within 6 months after autologous transplantation or
 - ii. within 1 year after allogeneic transplantation (regardless of immunosuppression)

- iii. greater than 1 year after allogeneic transplantation if still taking systemic immunosuppression or prophylactic antibiotics (e.g. for chronic graft versus host disease)

Note: if details of stem cell transplantation are unknown, patients who do not take systemic immunosuppression and do not take anti-infective prophylaxis are acceptable for enrollment and randomization.

- c. solid organ transplantation with receipt of systemic immunosuppression (any time)
- d. cytotoxic anti-cancer chemotherapy within the past three months (Note: next-of-kin estimate is acceptable)
- e. congenital immunodeficiency requiring antimicrobial prophylaxis (e.g. TMP-SMX, dapsone, antifungal drugs, intravenous immunoglobulin)
- f. receipt of one or more of the following in the indicated time period (see Appendix C):
 - i. within 6 months: prednisone, alemtuzumab, antithymocyte/antilymphocyte antibodies, or other immunosuppressive drugs associated with CMV reactivation

Note:

- If no information on these agents is available in the history and no direct or indirect evidence exists from the history that any condition exists that requires treatment with these agents (based on the investigator's assessment), the subject may be enrolled. For all drug information, next-of-kin estimates are acceptable. See Appendix C for commonly prescribed immunosuppressive agents. Information on the use of biologics with moderate immunosuppressive effect but no known effect on CMV are permitted and will be recorded in the CRFs.
- An average of >20mg/day of prednisone for the past 30 days prior to hospital admission. The total prednisone intake should be added and averaged over 30 days. For example, a patient taking 40mg/day for 14 days would not be excluded because $(40 \times 14) / 30 = 18.7$. Other steroids should be converted into prednisone equivalents. Additionally, any dose of corticosteroids given for any reason on or after hospital admission is acceptable.

2. Expected to survive < 72 hours (in the opinion of the investigator), or not committed to full intensive care support at the time of study enrollment (DNR but otherwise committed to full support is acceptable).
3. Unable to start receiving first dose of study drug within 120 hours after hospitalization (as measured from admission or time of transfer; subjects who are transferred from a chronic care ward, such as a rehabilitation unit, with an acute event are acceptable).
4. Pregnant or breastfeeding (either currently or expected within one month).

Note: for women of childbearing age (18-60 years, unless documentation of surgical sterilization [hysterectomy, tubal ligation, oophorectomy]), if a pregnancy test has not been done as part of initial ICU admission work-up (within 120 hours before enrollment), it will be ordered stat and documented to be negative before randomization. Both urine and blood tests are acceptable.
5. Absolute neutrophil count < 1,000/mm³ (if no ANC value is available, the WBC must be > 2500/mm³)

6. Use of anti-CMV drugs (cidofovir, letermovir, foscarnet, valganciclovir, ganciclovir) within seven (7) days of patient randomization.
7. Use of IVIG within four (4) weeks of patient randomization [103].
8. Currently intubated for airway protection only.
9. Currently enrolled in an interventional trial of an investigational therapeutic agent known or suspected to have anti-CMV activity or to be associated with significant known hematologic toxicity (prior approval required).
10. At baseline patients who have a tracheostomy, and have been receiving any positive pressure ventilation through it during the 30-day period prior to ICU admission.
11. Patients with Child Class C Cirrhosis.
12. Patients with severe (requiring home oxygen) pre-existing interstitial lung disease.
13. Allergy to ganciclovir
14. Incarcerated
15. Other, specify (e.g. clinician refusal)

